#### 9.7 **Screen failures**

Screen failures are defined as patients who consent to participate in the clinical study by signing the ICF, but do not fulfil all eligibility criteria and are not subsequently randomized in the study. A minimal set of screen failure information is required to ensure transparent reporting of screen failure patients. Minimal information includes documentation of signed and dated informed consent form (ICF), age, gender and reason(s) for screening failure.

Rescreening can be performed once if any of the following were reasons for screening failure or non-randomization (as judged by the Investigator):

- Practical reasons.
- Non-significant medical conditions (e.g. influenza, nasopharyngitis).
- Plasma or blood donation or use of prior medications outside allowed time windows.

For patients who are rescreened, a new screening number will be assigned and a new, signed ICF will be collected.

## 9.8 Patient withdrawal

### 9.8.1 *General withdrawal criteria*

Patients are free to discontinue their participation in the study at any time and for whatever reason without affecting their right to an appropriate follow-up investigation or their future care. If possible, the reason for withdrawal of consent should be documented.

Patients may be discontinued from the study at any time at the discretion of the Investigator.

Reasons for discontinuation include:

- Patient decision (withdrawal of consent)
- Severe non-compliance to study protocol procedures, as judged by the Investigator and/or Sponsor
- Permanent discontinuation of IMP. Temporarily treatment interruptions of  $\geq 3$  days may result in study discontinuation as judged by the Investigator and Sponsor.
- Patient is lost to follow-up. If a patient misses a scheduled visit and is repeatedly unable to be contacted, the patient will be withdrawn from the study.
- Significant AEs posing a risk for the patient, as judged by the Investigator and/or Sponsor
- Withdrawal of informed consent to the use of biological samples
- Pregnancy
- Death - Request an autopsy report
- Use of prohibited medication as judged by the Investigator and/or Sponsor
- The patient exhibits serious suicidality, in the clinical judgement of the investigator or according to criteria below:
  - Any suicidal behavior (i.e. actual attempt, interrupted attempt, aborted attempt, or preparatory acts or behavior)
  - Any suicidal ideation of type 4 or 5 in the C-SSRS (i.e. active suicidal thought with intent but without specific plan, or active suicidal thought with plan and intent)

### 9.8.2 *QTc withdrawal criteria*

A patient meeting the criteria below will be withdrawn from the study. The same QT correction formula will be used to determine discontinuation throughout the study.

- QTcF  $> 500$  msec
- Change from baseline: QTc  $> 60$  ms

Withdrawal decisions will be based on an average QTc value of triplicate ECGs. If an ECG demonstrated a prolonged QT interval, 2 more ECGs will be obtained over a brief period and

the averaged QTc values of the 3 ECGs used to determine whether the patient should be discontinued from the study.

### 9.8.3 *Liver chemistry withdrawal criteria*

Liver chemistry threshold stopping criteria have been designed to assure patient safety and to evaluate liver event etiology. Study treatment will be stopped for the individual patient if any of the following liver chemistry stopping criteria, defined in the U.S. Food and Drug Administration (FDA) Guidance on Drug-Induced Liver Injury [22], is met:

- Alanine aminotransferase (ALT) 3 x upper limit of normal (ULN) and total bilirubin  $\geq$  2xULN ( $>35\%$  direct bilirubin); **or** ALT 3xULN and INR  $> 1.5$ )

*NOTE: plasma bilirubin fractionation will be performed. Bilirubin is also measured via urine dipstick (a measurement of direct bilirubin, which would suggest liver injury).*

- ALT 5xULN.
- ALT 3xULN if associated with symptoms (new or worsening) believed to be related to hepatitis (such as fatigue, nausea, vomiting, right upper quadrant pain or tenderness or jaundice) or believed to be related to hypersensitivity (such as fever, rash or eosinophilia).
- Patients with ALT 3xULN **and**  $< 5xULN$  **and** bilirubin  $< 2xULN$ , who do not exhibit hepatitis symptoms or rash, will be allowed to continue study treatment as long as they are monitored weekly for 4 weeks.

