A follow-on Phase 2 study in DNP with 456 patients tested 3 doses of NLX-112 [0.5, 1.0, and 1.5 mg BID (1.0, 2.0, 3.0 mg/day)] vs placebo (Study CP201). Safety and tolerability in this study, which employed an 11-day up-titration period prior to and a 10-day down titration period after the 6-week fixed-dose period, were similar to the previous phase 2 study. Four SAEs occurred but none were related to NLX-112. Dizziness, headache, nausea and insomnia were the most common TEAEs and occurred predominantly during the up-titration period or the first fixed-dose week (Table 6.1-1). Please refer to the NLX-112 Investigators' Brochure for additional details on safety, tolerability and adverse events (AEs) in the NLX-112 phase 2 clinical program.

**Table 6.1-1 Most Common Drug-related TEAEs (incidence > 2% of patients) Listed By Number of Patients in Each Dose Group in Study CP201**

Preferred Term	PBO (N=112)	NLX-112 Groups		
		1 mg (N=113)	2 mg (N=114)	3 mg (N=117)
Dizziness	1 (0.9%)	8 (7.1%)	15 (13.2%)	15 (12.9%)
Nausea	4 (3.6%)	6 (5.3%)	12 (10.5%)	16 (13.7%)
Headache	3 (2.7%)	3 (2.7%)	6 (5.3%)	9 (7.7%)
Insomnia	-	3 (2.7%)	3 (2.6%)	6 (5.1%)

Preferred Term	PBO (N=112)	NLX-112 Groups		
		1 mg (N=113)	2 mg (N=114)	3 mg (N=117)
Withdrawal syndrome	1 (0.9%)	4 (3.5%)	4 (3.5%)	5 (4.3%)
Paresthesia	1 (0.9%)	3 (2.7%)	4 (3.5%)	2 (1.7%)
Vomiting	-	-	-	5 (4.3%)
Hypotension	-	3 (2.7%)	2 (1.8%)	2 (1.7%)
Accidental overdose	1 (0.9%)	3 (2.7%)	3 (2.6%)	2 (1.7%)
Hypertension	-	1 (0.9%)	1 (0.9%)	3 (2.6%)
Mood Swings	2 (1.8%)	-	2 (1.8%)	3 (2.6%)
ALAT increased	1 (0.9%)	1 (0.9%)	3 (2.6%)	-

Thus, based on Phase 1 and 2 study results, NLX-112 could be safely administered up to the dose of 3.0 mg/day with a progressive up-titration to maximize the tolerability of the drug and a down-titration to prevent withdrawal symptoms.

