Study day	Protocol Section	Day -28 to Day -5	Day 1	Day 7 ±1 day	Day 14 ±2 days	Day 21 ±2 days	Day 28 ±2 days	Day 42 ±2 days	Day 49 ±2 days	Day 70 ±7 days
Diary data collection 	11.3.3		X				X	X		
Wearable device data collection 	11.3.6		X				X	X		
L-DOPA challenge	11.3.1		X				X	X		
UDysRS	11.3.2		X				X	X		
Video taping (UDysRS)	11.3.2		X				X	X		
CGI-S/CGI-C 	11.3.5		X				X	X		
KPPS	11.4.1		X				X	X		
PDQ39	11.4.2		X				X	X		
HADS	11.4.3		X				X	X		
ICIQ-OAB	11.4.4		X				X	X		
ESS	11.4.5		X				X	X		
NLX-112 plasma concentration sampling	11.4.6				X	X	X	X		X
Drug accountability	10.5						X	X		X
Baseline symptoms	11.1.10	X								
Adverse events 	11.2.1						X			
Prior and concomitant medications	11.1.6						X			

CGI-S/CGI-C=Clinical Global Impression of Severity and Clinical Global Impression of Change, C-SSRS=Columbia Suicide Severity Rating Scale, ESS=the Epworth Sleepiness Scale, HADS=the Hospital Anxiety Depression Scale, ICIQ-OAB=the International Consultation on Incontinence Questionnaire Overactive Bladder Module,

KPPS=the King's Parkinson's disease Pain Scale, UPDRS=the Unified Parkinson's Disease Rating Scale, MMSE=Mini Mental Status Exam, PDQ39=the Parkinson's disease Quality of Life Scale (39-item), UDysRS=the Unified Dyskinesia Rating Scale

1. Also early withdrawal follow-up visit
2. Confirmation of eligibility
3. Blood pressure (including orthostatic hypotension assessment), pulse, respiratory rate and temperature. At screening and baseline (Visit 1 and Visit 2), vital signs to assess orthostatic hypotension will be conducted in triplicate, 15-20 minutes apart, with the average of the 3 assessments used for exclusion.
4. Body weight at Visit 1 and Visit 9. Height at Visit 1 only.
5. The Modified Hoehn and Yahr scale will be used to establish the PD stage of the patient.
6. Women of child-bearing potential only.
7. Hematology, coagulation, serum biochemistry and urinalysis.
8. C-SSRS: the baseline scale will be used at the first assessment (screening, Visit 1) and the follow-up scale will be used at all subsequent visits.
9. UPDRS - Screening: part IV only. Other visits: parts I-IV
10. PD Home Dyskinesia Diary: 2 consecutive 24-hour diaries taken prior to the visits indicated above.
11. Wearable data collection will take place during a 2-day period prior to the visits indicated above.
12. CGI-S at baseline (Day 1, Visit 2), CGI-C at other visits.

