**Table 11.2-1 Safety laboratory parameters**

Category	Parameter
Clinical chemistry	Alanine aminotransferase (ALT)
	Albumin
	Alkaline phosphatase (ALP)
	Aspartate aminotransferase (AST)
	Bilirubin (total and conjugated)
	Calcium
	Chloride
	C-reactive protein (CRP) (screening only)
	Creatine phosphokinase (CPK)
	Creatinine (eGFR included)
	Gamma glutamyl transpeptidase (GGT)
	Glucose
	Phosphate
	Potassium
	Sodium
	Urea (nitrogen)
	Uric acid
Hematology	Hematocrit
	Hemoglobin (Hb)
	Platelet count
	Red blood cell (RBC) count
	White blood cell (WBC) count with differential count
	Mean corpuscular volume (MCV)
	Mean corpuscular hemoglobin (MCH)
	Mean corpuscular hemoglobin concentration (MCHC)
Coagulation	Activated Partial Thromboplastin Time (APTT)
	Prothrombin Complex International Normalized Ratio (PK[INR])
Urinalysis (dip stick)	Bilirubin
	Blood
	Erythrocytes
	Glucose
	Ketones
	Leucocytes
	Nitrites
	pH
	Albumin
Pregnancy test	Urine pregnancy test at screening 

 Females of child-bearing potential only

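### Liver rule (Protocol 9.8.3): the permission to continue at ALT 3–5xULN omits INR and so contradicts the mandatory stop for raised ALT with INR > 1.5

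*Protocol*

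**What the plan says.** Section 9.8.3 opens with a mandatory rule: "Study treatment will be stopped for the individual patient if any of the following liver chemistry stopping criteria" is met. Four bullets follow.

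- **Bullet 1** has two limbs. One is ALT 3xULN with total bilirubin at least 2xULN (more than 35% direct). The other is "ALT 3xULN and INR" above 1.5. The INR limb carries no bilirubin or symptom condition.
- **Bullet 2** is ALT 5xULN.
- **Bullet 3** is ALT 3xULN with symptoms attributed to hepatitis, or "believed to be related to hypersensitivity (such as fever, rash or eosinophilia").
- **Bullet 4** is not a stopping criterion. It covers patients with ALT 3xULN and below 5xULN and bilirubin under twice ULN, "who do not exhibit hepatitis symptoms or rash, will be allowed to continue study treatment as long as they are monitored weekly". The monitoring period is 4 weeks.

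Section 9.8.3 does not say how bullet 4 relates to bullets 1 to 3. INR is in the coagulation panel (Table 11.2-1), and the safety laboratory is defined in footnote 7 of the schedule of events (Table 8.1-1) as "Hematology, coagulation, serum biochemistry and urinalysis".

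**The concern.** Bullet 4 restates a limit from each of the other bullets: bilirubin from bullet 1, the 5xULN ceiling from bullet 2, and symptoms or rash from bullet 3. It therefore reads as a complete set of conditions for staying on treatment. INR is the one stopping variable that it leaves out entirely. On its own words it lets dosing go on in a patient whose ALT and INR are both raised, which is one of the two combinations in the first stopping criterion.

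The rule decides whether a patient with possible liver injury keeps taking the drug, in a trial whose primary objective is safety and tolerability. A site holding such a laboratory report needs one answer.

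**Working it through.** The plan states no figure here to reproduce. The check is to apply the bullets to the same patient and see whether they agree.

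**Reading assumed.** 3xULN and 5xULN are taken as at least 3 and at least 5, because no inequality sign appears in the available text. The worked case uses ALT 4xULN, between the two limits, so it does not depend on this.

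**Worked case:** ALT 4xULN, bilirubin 1xULN, INR 1.8, no symptoms.

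- Bullet 1, INR limb: ALT 4 ≥ 3, yes; INR 1.8 > 1.5, yes. Result: **stop**.
- Bullet 4: ALT 4 lies between 3 and 5, yes; bilirubin 1 < 2, yes; no hepatitis symptoms or rash, yes. Result: **continue**.

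**All cases that bullet 4 permits.** Within bullet 4, ALT is 3 to below 5xULN, bilirubin is below 2xULN, and hepatitis symptoms and rash are absent. Two things that bullets 1 and 3 use can still vary: INR, and other hypersensitivity signs (fever or eosinophilia attributed to hypersensitivity).

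| INR | Other hypersensitivity signs | Bullets 1–3 | Bullet 4 |
|---|---|---|---|
| ≤ 1.5 | no | no stop | continue |
| ≤ 1.5 | yes | stop (bullet 3) | continue |
| > 1.5 | no | stop (bullet 1) | continue |
| > 1.5 | yes | stop (bullets 1 and 3) | continue |

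Three of the four rows conflict. These are logical combinations, not patient frequencies. Both rows with INR above 1.5 conflict, and in the third row INR is the only cause. Adding INR ≤ 1.5 to bullet 4 leaves two permitted rows with one conflict. Excluding the other hypersensitivity signs as well leaves one permitted row and no conflict.

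The second row is a weaker point. It vanishes if bullet 4's mention of hepatitis symptoms or rash is taken as shorthand for everything in bullet 3.

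**How often.** Table 6.1-1 (Study CP201, diabetic neuropathy) lists "ALAT increased" as a drug-related event:

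- 2 mg/day: 3/114 = 2.63% (exact 95% CI 0.55% to 7.50%). For 16 active patients: 16 × 0.0263 = 0.42 (0.09 to 1.20).
- All NLX-112 doses: (1 + 3 + 0)/(113 + 114 + 117) = 4/344 = 1.16% (0.32% to 2.95%). For 16 patients: 0.19 (0.05 to 0.47).
- Placebo: 1/112 = 0.9%.

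These count drug-related ALT increases of any size, with no ULN multiple and no INR. The documents give no rate for ALT 3–5xULN together with INR above 1.5.

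**Whether it would be seen.** ALT, bilirubin and INR are all in the safety laboratory, which Table 8.1-1 schedules at four on-treatment visits after baseline: Visits 4, 5, 6 and 7 (Days 14, 21, 28 and 42).

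**The case against.** The best defence is that the lead-in already settles the matter. It is mandatory and applies if any one criterion is met, whereas bullet 4 only permits. A permission does not cancel a stop that has been triggered, so bullet 4 would naturally describe the patients left over after bullets 1 to 3. That is the more sensible reading, and it limits the practical risk. But it has to be inferred. Taken literally, the lead-in would turn bullet 4 itself into a reason to stop, which cannot be meant. The reader must therefore treat bullet 4 as an exception without being told which bullets it overrides.

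Other safeguards exist. Section 9.8.1 says "Patients may be discontinued from the study at any time at the discretion of the Investigator", clinically significant laboratory abnormalities are reported as adverse events, patients with clinically significant liver disorder are excluded, and bullet 4 itself demands weekly monitoring. These make continued dosing at ALT 4xULN with INR 1.8 unlikely. They do not say which of the two rules governs.

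The layout of the list may also have been altered in text extraction, so the placement of bullet 4 inside the list is less certain than its wording. The missing INR condition does not depend on placement.

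Finally, the ALT event rates do not measure the conflicting combination. Because they are limited to drug-related events, they are not an upper bound on ALT elevations from any cause either. That is correct; they serve only as context.

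**Conclusion.** The concern holds, as a minor correction to a safety rule. For ALT 3xULN to below 5xULN with INR above 1.5, bilirubin below 2xULN and no symptoms, Section 9.8.3 gives two opposite instructions and no order of precedence. The frequency is unknown and expected to be low. Even any drug-related ALT increase would be expected in well under one of about 16 active patients on the point estimates, provided the diabetic neuropathy rates carry over. No endpoint, analysis, sample size or error rate is touched. The overlap for fever or eosinophilia is secondary and depends on how bullet 4 is read.

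**What to change.** Take bullet 4 out of the stopping list and make it a separate paragraph, for example:

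> A patient with ALT of at least 3xULN but below 5xULN may stay on study treatment, with weekly monitoring for 4 weeks, only if none of the stopping criteria above is met, bilirubin is below 2xULN, INR is 1.5 or lower, and there is no hepatitis symptom, rash or other sign attributed to hypersensitivity (for example fever or eosinophilia).

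This removes every conflict in the table above. It costs one sentence in a protocol amendment and a notice to the sites; INR is already measured.

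The same amendment could close a neighbouring gap. A symptom-free patient with ALT 3–5xULN, INR of 1.5 or lower, and bilirubin at or above 2xULN with no more than 35% direct falls under neither the stop nor the permission. The new sentence keeps such a patient outside the permission, and the sponsor can state the intended action.

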### 9.8.4 *Procedures for discontinuation of a patient from the study*

A patient who prematurely discontinues participation in the study will always be asked about the reason(s) for discontinuation and the presence of any AEs. If a patient withdraws consent, the Investigator must ask the patient if he/she is willing, as soon as possible, to be assessed according to the procedures scheduled for the final follow-up visit (Visit 9). If the patient withdrew consent, was non-compliant, or was lost to follow-up, no further follow-up will take place after the final clinical evaluation. The Sponsor will determine on a case-by-case basis if a patient who withdraws for other reasons requires follow-up after the final clinical evaluation. Any ongoing AEs will be followed as described in Section 11.2.1.15. Pregnancies will be followed as described in 11.2.1.16.

The primary reason for discontinuation/early withdrawal must be specified in the eCRF and final drug accountability must be performed.

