## 6.3 Risk/benefit assessment

### 6.3.1 *Potential risks*

In prior clinical studies of NLX-112, the most frequently reported undesirable treatment effects were dizziness, somnolence, headache, nausea, and malaise; these effects are consistent with the pharmacological profile of NLX-112. These effects occurred mostly during the first days of treatment and were most frequent at the highest doses of study drug (i.e.,  $\geq 3.0$  mg/day).

The study of the tolerability and safety of NLX-112 administered as multiple doses after an adaptive dose titration in healthy subjects showed that progressive up-titration, and adjusting dose escalation based on individual tolerability, allowed some healthy men to tolerate 10 mg/day, when administered as 5 mg BID.

Abrupt discontinuation of NLX-112 after multiple daily dosing of 3.0 mg/day or higher was associated with the sporadic occurrence of withdrawal symptoms (mainly nightmare, anxiety, hallucination, and euphoric mood) which were reduced in severity with progressive down-titration.

Undesirable hemodynamic effects (i.e., decrease in blood pressure and postural hypotension) were observed in some elderly subjects.

Thus, based on prior human experience, NLX-112 can be safely administered up to the dose of 3.0 mg/day (1.5 mg BID), with a progressive up-titration to maximize the tolerability of the drug and a down-titration regimen after the fixed dose period to minimize potential withdrawal symptoms.

In cases of accidental overdose, standard supportive measures should be adopted as required. For further information regarding overdosing, refer to Section 11.2.1.17.

Each patient will be provided with a patient information card with information about the patient's participation in a study, see Section 14.4.

The Principal Investigator at the research clinic will ascertain that adequate facilities and procedures are available to handle emergency situations should they occur during the study.

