**Down-titration period (2 weeks, down-titration by 0.25 mg/day every 2 days):**

- Days 43-44 (start of down-titration period [1.75 mg/day])
- Days 45-46 (1.5 mg/day)
- Days 47-48 (1.25 mg/day)
- Days 49-50 (1 mg/day)
- Days 51-52 (0.75 mg/day)
- Days 53-54 (0.5 mg/day)
- Days 55-56 (0.25 mg/day)

Patients in the placebo arm will follow the same dose escalation, constant dose and down-titration schedule, but will be taking the matching placebo tablets. Patients who have intolerable AEs during the 28-day up-titration period will be allowed to return to the previous tolerated dose at the discretion of the Investigator, or they may withdraw from the study if they so choose.

Each patient is expected to participate in the study for approximately 10 weeks, not including screening. Patients will be treated with IMP for a total of 8 weeks (56 days).

The timing of events is summarized in Table 8.1-1. Study assessments are described in Section 11.

Table 8.1-1 Schedule of events

Study visit number		Visit 1	Visit 2	Visit 3	Visit 4	Visit 5	Visit 6	Visit 7	Visit 8	Visit 9
Study period		Screening	Baseline	Phone Safety Visit	Clinic Safety Visit	Clinic Safety Visit	Clinic Efficacy Visit	Clinic Efficacy Visits	Phone Safety Visit	Follow-up Clinic Visit 
Study day	Protocol Section	Day -28 to Day -5	Day 1	Day 7 ±1 day	Day 14 ±2 days	Day 21 ±2 days	Day 28 ±2 days	Day 42 ±2 days	Day 49 ±2 days	Day 70 ±7 days
Informed Consent	14.3	X								
Eligibility criteria	9.4 & 9.5	X	X 							
Demographics	11.1.3	X								
Vital signs 	11.2.3	X	X		X	X	X	X		X
Physical examination	11.2.2	X								X
Body weight and height 	11.1.4	X								X
Hoehn and Yahr scale 	11.1.8	X	X							
Medical and psychiatric history	11.1.5	X								
Pregnancy test 	11.1.7	X	X							X
12-lead ECG	11.2.4	X	X		X	X	X	X		X
Safety laboratory 	11.2.6	X	X		X	X	X	X		X
MMSE	11.1.9	X								
C-SSRS 	11.2.5	X	X		X	X	X	X		X
UPDRS 	11.3.1	X	X				X	X		X
Diary and wearable device training	11.3.3&11.3.6	X	X							
Randomization	9.9		X							
Study drug dispensing	10.5		X				X	X		
Treatment (Day 1 - Day 56)	10.6					X				

Study visit number		Visit 1	Visit 2	Visit 3	Visit 4	Visit 5	Visit 6	Visit 7	Visit 8	Visit 9
Study period		Screening	Baseline	Phone Safety Visit	Clinic Safety Visit	Clinic Safety Visit	Clinic Efficacy Visit	Clinic Efficacy Visits	Phone Safety Visit	Follow-up Clinic Visit 

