#### *11.2.1.6 Time period and frequency for collecting adverse events*

All AEs (including SAEs) will be collected from the start of IMP administration until the end-of-study visit.

Any AE with start date on the day of IMP administration will, if possible, be recorded with start time.

At the end-of-study visit, information on new AEs or SAEs, if any, and stop dates for ongoing events must be recorded as applicable.

Investigators are not obligated to actively seek AEs or SAEs after conclusion of the study participation. However, if the Investigator learns of any SAE, including a death, at any time after a participant has been discharged from the study, and he/she considers the event to be reasonably related to the study intervention or study participation, the Investigator must promptly notify the Sponsor.

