#### *11.2.1.15 Treatment and follow-up of adverse events*

Patients with AEs that occur during the study must be treated according to daily clinical practice at the discretion of the Investigator.

AEs must be followed up until resolution or to the end-of-study visit, whichever comes first. At the end-of-study visit, information on new AEs, if any, and stop dates for previously reported AEs must be recorded (if known). AEs assessed as stable by the Investigator at the end-of-study visit will not have to be followed up until resolution.

It is the responsibility of the Investigator to follow up on all SAEs until the patient has recovered, stabilized, or recovered with sequelae, and to report to the Sponsor all relevant new information using the same procedures and timelines as those for the initial report. Relevant information includes discharge summaries, autopsy reports, and medical consultation.

Patients who withdraw from the study due to an AE must be followed by the Investigator for 30 days after the last dose of NLX-112 or until the AE is considered resolved or stabilized.

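### For patients who leave early, the protocol sets no minimum time off drug before the final safety visit, at which adverse event collection ends

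*Protocol*

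**What the plan says.** **Completers.** Protocol 8.1: "Patients will be treated with IMP for a total of 8 weeks (56 days"), the last 14 of them (Days 43–56) a stepwise down-titration. Table 8.1-1 puts Visit 9 at Day 70 ± 7 days.

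**Early leavers.** Footnote 1 of Table 8.1-1 makes Visit 9 the early-withdrawal visit as well and gives no timing for that use. Section 9.8.1 lists "Permanent discontinuation of IMP" among the reasons for leaving the study. Under 9.8.4 everyone who leaves early is asked about the reason and about AEs. A patient who withdraws consent is asked whether he or she is "willing, as soon as possible, to be assessed according to the procedures scheduled for the final follow-up visit (Visit 9"). After withdrawal of consent, non-compliance or loss to follow-up, "no further follow-up will take place after the final clinical evaluation". For other reasons the sponsor decides case by case.

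**AE collection.** Section 11.2.1.6: "All AEs (including SAEs) will be collected from the start of IMP administration until the end-of-study visit". After that, investigators need not look for events, although a related SAE that they learn of must still be notified. The note to SAP Figure 1 models end of study as taking place at the patient's last participation.

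**Withdrawals due to an AE.** Under 11.2.1.15 these patients "must be followed by the Investigator for 30 days after the last dose of NLX-112 or until the AE is considered resolved or stabilized".

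**Withdrawal reactions.** Section 6.1.3 makes safe dosing conditional on a slow up-titration and "a down-titration to prevent withdrawal symptoms". Section 6.3.1 adds: "Abrupt discontinuation of NLX-112 after multiple daily dosing of 3.0 mg/day or higher was associated with the sporadic occurrence of withdrawal symptoms".

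**The concern.** Safety and tolerability are the primary objective, and reactions on stopping the drug are a named risk. Such a reaction begins after the last dose, so it is a new AE that is recorded only if collection is still open. For completers it stays open for a defined period off drug. For those who leave early, the closing date follows from a visit whose distance from the last dose is nowhere set. In the one case where timing is mentioned, the instruction is to hold the visit promptly.

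The planned arms are about 16 and 8 patients. A single patient with an unrecorded event changes an incidence by 1/16 = 6.25 percentage points on NLX-112 or 1/8 = 12.5 points on placebo.

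**Working it through.** **1. The plan's own timeline.** Up-titration of 28 days, constant dose of 14 and down-titration of 14 give 28 + 14 + 14 = 56 treatment days. Day 70 / 7 = 10.0 weeks, matching the stated participation of about 10 weeks. Time off drug at Visit 9 is 70 − 56 = 14 days; the ±7-day window gives 63 − 56 = 7 to 77 − 56 = 21 days.

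**2. Washout.** The half-life is 34 to 41 h (Protocol 6.1.3). I assume simple mono-exponential decline, with the share remaining = 2^(−24d/T) after d days. As a conventional benchmark, five half-lives take 5 × 34 / 24 = 7.1 days to 5 × 41 / 24 = 8.5 days.

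**3. Drug left at the final visit.** The delay for early leavers is not stated, so the 1-, 2-, 3- and 7-day rows are assumptions for them.

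| Days since last dose | Half-lives elapsed | Share left |
|---|---|---|
| 1 | 0.6–0.7 | 61–67% |
| 2 | 1.2–1.4 | 38–44% |
| 3 | 1.8–2.1 | 23–30% |
| 7 (also a completer seen on Day 63) | 4.1–4.9 | 3–6% |
| 14 (completer seen on Day 70) | 8.2–9.9 | 0.1–0.3% |

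Worked example: 2^(−48/34) = 0.38 and 2^(−48/41) = 0.44. A visit less than about 7.1 to 8.5 days after the last dose falls before five half-lives.

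**4. Which early leavers are affected.**

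| Reason for leaving | Visit timing | Afterwards |
|---|---|---|
| Consent withdrawn | Promptly, if willing | No follow-up |
| Non-compliance | Not stated | No follow-up |
| Lost to follow-up | Not applicable | No follow-up |
| AE | Not stated | 30 days after last dose, or until that AE resolves or stabilizes |
| Other | Not stated | Sponsor decides case by case |

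No row sets a minimum off-drug interval for collecting new AEs. The AE row comes closest, but its two limbs are joined by an alternative, so the second can be read as ending follow-up sooner. It also does not say that new AEs are collected.

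**5. Is the risk relevant at these doses?** Table 6.1-1 (Study CP201) lists drug-related withdrawal syndrome in 4/113, 4/114 and 5/117 patients at 1, 2 and 3 mg/day. Pooled, that is 13/344 = 3.8%, against 1/112 = 0.9% on placebo. Fisher's exact test gives p = 0.20 pooled and p = 0.37 for 2 mg alone. The contrast rests on one placebo event and shows only that zero risk cannot be assumed at 2 mg/day or below.

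**The case against.** Several safeguards exist. Everyone leaving early is asked about AEs, ongoing AEs are followed under 11.2.1.15, SAEs are followed until recovery or stabilization, and a related SAE learned of later must be notified. These narrow the gap. Apart from that SAE notification, they concern events already present when the patient leaves, so a non-serious reaction starting later is not secured.

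Four stronger readings are tempting, and the documents do not support them.

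- **That every early stopper is seen promptly.** That timing is written only for withdrawal of consent. For the rest the timing is simply open.
- **That the missed events fall mainly on NLX-112 and flatter its safety.** A reader might infer this from dizziness in CP201 (13.2% at 2 mg against 0.9% on placebo). But incidence is not stopping. In the 12-week study at 2 mg/day only one NLX-112 patient withdrew because of a treatment-emergent AE (6.1.3), and 8.1 allows return to the previous tolerated dose. Patients who do stop for intolerance recorded as an AE are the best-covered group under 11.2.1.15. Nothing shows that consent withdrawal or non-compliance is commoner on active drug.
- **That early stoppers stop abruptly.** The withdrawal sections neither require nor exclude a taper. Immediate stopping is written for pregnancy (11.2.1.16), and stopping is required under the liver criteria (9.8.3), but there is no general statement.
- **That 6.3.1 conflicts with Table 6.1-1.** The first concerns abrupt stopping at 3.0 mg/day or more; the second comes from a study with a 10-day down-titration. Both can be true.

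The remedy is also weakest where the text is clearest: patients who withdraw consent may refuse contact, and those lost to follow-up cannot be reached.

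**Conclusion.** The point holds as a gap in the rule for ending AE collection. Completers get a nominal 14 days off drug after a taper; early leavers get no defined minimum, and further follow-up is ruled out after consent withdrawal or non-compliance. New off-drug events, including withdrawal reactions, may be missed in some of them.

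The residual-drug figures rest on assumed visit delays and mono-exponential decline; a completer seen at the early edge of the window has the same 3–6% left as an early leaver seen at 7 days. The conclusion also takes the early-withdrawal visit to be the end-of-study visit for that patient, which fits footnote 1 of Table 8.1-1 and the note to SAP Figure 1. The number of early leavers is not given, so neither the direction nor the size of an effect on the arm comparison can be derived.

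**What to change.** In Protocol 9.8.4, 11.2.1.6 and footnote 1 of Table 8.1-1, define the end of AE and SAE collection relative to the last dose for every patient, whatever the reason for leaving. Match the completers' nominal 14 days off drug. If the early-withdrawal visit falls sooner, complete the period by a telephone contact, provided the patient has not refused it. State in 11.2.1.15 whether new AEs are collected during the follow-up of patients withdrawn because of an AE.

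The cost is some wording and about one call per early leaver. Some who withdraw consent will decline, so the gap will be reduced rather than closed.

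Separately, sections 6.1.3, 6.3.1, 8.1, 9.8.1, 9.8.3 and 11.2.1.16 should be reconciled on whether the down-titration that the risk assessment relies on applies to patients who stop early. That clinical rule is for the sponsor to decide.
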